It is hypothesized that efficacy and safety of medical expulsive therapy, containing tamsulosin and silodosin, is almost the same and silodosin can be used with the same efficacy for the treatment of lower urinary tract calculi.

Alternative Hypothesis:

Silodosin is better than Tamsulosin in efficacy and safety.

OPERATIONAL DEFINITIONS:

STONE CLEARANCE:

Stone clearance will be defined as no evidence of stone on follow up X-ray KUB imaging at 4 weeks .

ANCILLARY PROCEDURES:

Additional urological procedures needed to remove the same stone for which medical expulsive therapy was given if it fails to remove the stone completely.

SIDE EFFECTS:

Any undesirable effect noticed after prescription of the drug including but not limited to abnormal ejaculation, headache, orthostatic hypotension, backache and gastritis etc.

MATERIALS AND METHODS:

STUDY DESIGN:

Prospective randomized control trial.

STUDY SETTING:

Outpatient department of Sir Ganga Ram hospital, Lahore.

DURATION OF STUDY:

18 months.

DURATION OF TREATMENT:

Four weeks.

SAMPLE SIZE:

Using the open-epic software, the sample size was estimated. The minimum sample size that we require is 208 patients with ureteric stone who fulfil the inclusion criterion with 104 in one group receiving tamsulosin and 104 in silodosin group (1:1 ratio) with an inflation of 10 percent for estimated loss to follow up, with an anticipated expulsion rate ranging from 58-64 percent in tamsulosin group and 78-83 percent in silodosin group with a risk difference of 19 to achieve a power of 80 percent and a level of significance of 5 percent.

SAMPLING TECHNIQUE:

Patients visiting the outpatient department of Sir Ganga Ram hospital will be selected by simple random sampling, fulfilling the inclusion criteria.

SAMPLE SELECTION:

Adult male and female patients fulfilling the inclusion criteria will be assigned into two groups by random allotment, 1^{st} group will be given Tamsulosin and 2^{nd} group will be given Silodosin for four weeks.

INCLUSION CRITERIA:

Following factors make up the inclusion criteria for this study.

- Patients between ages 18 years 55 years.
- Solitary unilateral ureteral stone
- Stone sizes less than 10 mm measured on non-contrast computed tomography of kidney, ureter and bladder.
- Stones being treated primarily with medical expulsive therapy
- Radio opaque Stone

EXCLUSION CRITERIA:

The presence of following factors will exclude the patients from our study:

- Pregnancy
- Untreated UTI

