- Bleeding disorders
- Obstruction distal to stone
- Serum Creatinine > 1.3 mg/dl in males and > 1.2 mg/dl in females.
- Congenital renal anomaly/ skeletal malformation
- Previous treatment for the same stone (PCNL/ URS / push back)
- Solitary Kidney
- Prior JJ stent insertion
- Bilateral ureteral stone

DATA COLLECTION AND PROCEDURE:

The protocol will be submitted to Ethical review committee for review and only once the permission is granted, the study will be started. Patients will undergo standard procedure like detailed history taking, examination and routine investigations. Once decided that the patient will undergo MET, the patient will be explained in detail about medications, their potential side effects, follow up and the potential indications for early follow up. Our study will not change any standard process in place except the randomization between Tamsulosin and Silodosin. The data will be kept confidential as a top priority. Only principal investigator and co-principal investigator will have access to the data.

All patients as per inclusion and exclusion criteria as described above will be included in the study. The CT scan (non contrast computed tomography) will be done on (machine parameters at Ganga ram). Only patients with radioopaque stones will be included. Patients falling into the inclusion criteria will be explained about the study and once they agree to participate in study, randomization will be done. Demographic data including patients' age and comorbid, stone-related data including size, location, laterality and number of stones and duration of symptoms will be recorded. The patient will be given either Capsule Tamsulosin 0.4 mg once daily at night or Tablet Silodosin 8 mg once daily at night based on the group assigned. The patient will also be explained about the reasons for follow up earlier than four weeks including fever, persistent pain or gross hematuria. The patients will be called for follow up at 4 weeks with an X-ray KUB without bowel preparation. We will note if the stone has passed or not.

ETHICAL CONSIDERATION:

The funds for supporting this research will be provided by department of pharmacology and therapeutic FJMU, Lahore. Informed consent will be taken from patients prior to research.

DATA ANALYSIS PROCEDURE:

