Only a very tiny percentage of patients reported experiencing abnormal ejaculation; 2 individuals on tamsulosin (66.7%) and 1 patient on silodosin (33.3%) reported this side event. Again, this points to an increased chance of this specific adverse effect in Tamsulosin users, but the numbers are too low to make any firm conclusions. Another side effect that was identified involved headaches, which were seen by 4 individuals on silodosin (44.4%) and 5 patients on tamsulosin (55.6%). Headaches were marginally more common among Tamsulosin users compared to Silodosin users, similar to orthostatic hypotension.

Many urologists agree when it comes to the incidence of retrograde ejaculation that it is an indication of therapy efficacy rather than a negative effect. It seems that silodosin relaxes the smooth muscles in the genital and lower urinary tracts sufficiently to cause a retrograde ejaculation. Retrograde ejaculation was more common in the individuals who experienced the most alleviation from lower urinary tract symptoms, which was consistent with this conclusion. This finding implies that the retrograde ejaculation is, in fact, a passive marker of the smooth muscle relaxation brought on by silodosin(32).

Typically, nonselective $\alpha 1$ adrenoceptor antagonists such doxazosin and terazosin are linked to orthostatic hypotension. Nonetheless, in clinical trials, silodosin was linked to a modest incidence of orthostatic hypotension. According to the combined analysis of the US and European studies, 1.1% of patients receiving a placebo and 1.3% of patients receiving silodosin experienced orthostatic hypotension(48).

When compared to Tamsulosin, Silodosin is linked to a larger incidence of retrograde ejaculation but a reduced incidence of peripheral vasodilation-related adverse effects, such as orthostatic hypotension and dizziness, according to a retrospective review conducted by Imperatore et al(49).

In our study comparing the effects of Tamsulosin and Silodosin on patients, it was discovered that only 38.1% of those receiving Silodosin needed analgesics to ameliorate ureteric pain. On the other hand, 61.9% of patients receiving Tamsulosin required analgesic intervention, which is a far larger percentage. This significant difference raises the possibility that silodosin is more successful in treating ureteric stones and it also lowers their need for extra painkillers.

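### Capsule and tablet are distinguishable and no masked outcome assessment is described; reading the 4-week film before the allocation is opened is a cheap safeguard

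*Combined protocol and SAP*

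**What the plan says.** All references are to the combined protocol and SAP.

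- **Design and allocation.** The Study Design entry reads "Prospective randomized control trial". Under Sample Selection, patients "will be assigned into two groups by random allotment". Neither entry mentions masking.
- **Products.** Data Collection and Procedure specifies "Capsule Tamsulosin 0.4 mg once daily at night or Tablet Silodosin 8 mg once daily at night based on the group assigned". No placebo or double-dummy is described. Before treatment "the patient will be explained in detail about medications, their potential side effects, follow up".
- **Efficacy outcome.** Under Operational Definitions, "Stone clearance will be defined as no evidence of stone on follow up X-ray KUB imaging at 4 weeks". Data Collection and Procedure adds only "We will note if the stone has passed or not". The reader is not identified, and nothing is said about what the reader knows.
- **Safety outcome.** Side effects are "Any undesirable effect noticed after prescription of the drug". The plan does not say who notices them or how they are asked about.
- **Data access.** Access is limited to the principal and co-principal investigators.
- **Hypothesis.** The alternative is directional: silodosin is better in both efficacy and safety.

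The only references to single blinding, in the Literature Review and Discussion, describe a separate paediatric trial.

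**The concern.** The products can be told apart and the study team records the result, so nothing in the plan stops the person judging an outcome from knowing the arm. The expected direction is stated in advance. Four records are exposed: whether a small stone is still visible on a plain film taken without bowel preparation, which side effects are elicited, whether analgesics were needed, and when the stone passed.

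The Conclusion claims an advantage for silodosin in expulsion rate and time, side effects and analgesic need. The Discussion goes further on analgesics: "This significant difference raises the possibility that silodosin is more successful in treating ureteric stones". If any of these records leaned towards the expected answer, the claims would lean with them, and a larger sample would not correct it.

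**Working it through.** **1. The plan's own design figure, and whether the fix alters it.** Inputs from Sample Size: risk difference 19 points, power 80%, significance level 5% (two-sided assumed), 10% loss, 208 patients. The exact pair of rates is not stated. Taking 59% v 78%, with mean rate 0.685:

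n = [1.96·√(2·0.685·0.315) + 0.842·√(0.59·0.41 + 0.78·0.22)]² / 0.19² = 92.6, so 93 per arm.

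93 / 0.90 = 103.3, so 104 per arm and 208 in total, which matches. Masked assessment changes none of these inputs, so 208 stands.

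**2. Illustration of biased film reading.** The misreading rates and the 70% clearance rate are assumptions; neither comes from the documents. The 94 per arm is 104 less 10% (93.6, rounded). With true clearance p in both arms and a fraction f of residual stones called cleared in one arm only, the apparent rate there is p + f(1 − p). The chance of a significant result favouring that arm is the normal upper tail beyond

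z = (1.96·SE₀ − d) / SE₁,

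where d is the false difference and SE₀ and SE₁ are the pooled and unpooled standard errors.

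| True clearance | f | Apparent rates | z | False significant result |
|---|---|---|---|---|
| 70% | 0 | 70% v 70% | 1.96 | 2.5% |
| 70% | 10% | 70% v 73% | (0.1291 − 0.03)/0.0658 = 1.51 | 6.6% |
| 70% | 20% | 70% v 76% | (0.1269 − 0.06)/0.0646 = 1.04 | 15.0% |
| 61% | 10% | 61% v 64.9% | 1.41 | 8% |
| 61% | 20% | 61% v 68.8% | 0.84 | 20% |

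Over the plan's anticipated tamsulosin range of 58–64%, the f = 20% case gives 18–22%.

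**3. Where the reported efficacy contrast lies.** The Time for removal rows in the Results table sum to 6 + 14 + 57 = 77 (tamsulosin) and 52 + 37 + 13 = 102 (silodosin). That is all 179 analysed patients. On these figures both arms show removal in every patient by 28 days, so the contrast is one of timing. A single 4-week film cannot supply timing, and the plan does not say how timing was obtained.

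**4. Side effects.** A Pearson chi-square on the reported table (none 61 v 91; orthostatic hypotension 9 v 6; abnormal ejaculation 2 v 1; headache 5 v 4) gives 3.54 on 3 df, p = 0.315, as the Results text states. Grouped as any side effect, it is 16/77 (20.8%) v 11/102 (10.8%): uncorrected p = 0.064, Fisher p = 0.090. Neither analysis reaches the plan's 0.05 threshold, yet the Conclusion says that silodosin patients reported fewer side effects.

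**5. Analgesic use.** 26/77 (33.8%) v 16/102 (15.7%): difference 18.1 points, Newcombe 95% CI 5.4 to 30.6, uncorrected p = 0.005 as reported. The same table gives p = 0.001 between the arms for laterality, time from symptoms to CT, stone position and water intake. The 18.1 points therefore cannot be attributed to lack of masking.

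**The case against.** The strongest case on the other side has five parts.

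- **Knowledge of the arm is not documented.** A reader might infer that outcomes were judged with allocation known. The text shows only that the products differ and that the team noted the result. It does not say who read the films or what they knew. This stands, so the point is limited to masking not being described.
- **Self-report is not documented either.** A reader might take side effects and analgesic use to be wholly unmasked patient reports. The plan does not say how either was recorded, and orthostatic hypotension could have been measured. This also stands.
- **Biased film reading cannot explain the reported efficacy result.** With every analysed patient recorded as cleared by 28 days, there is no clearance difference for misread films to have produced. This stands for the reported data. The planned outcome is still clearance on a film, and the plan leaves its reading unprotected. Restricting entry to radio-opaque stones reduces doubtful readings without removing them.
- **The analgesic gap is not a measure of bias.** This stands, given the imbalances listed above.
- **The remedy is late and partial.** Results are already reported, patients know their product and may disclose it, and someone must keep the list from the reader. All true. But retained films can still be re-read, and with two investigators holding the data, one can keep the list while the other reads. Whether this needs no extra staff cannot be confirmed from the documents.

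The Results section does concede that the side-effect differences may be chance, and the Discussion calls the ejaculation numbers too low for firm conclusions. The Conclusion drops both cautions.

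**Conclusion.** The point holds in limited form. The arms receive distinguishable products, no masked assessment of any outcome is described, and the hypothesis is directional. Assessors may therefore know the arm, and a low-cost safeguard for the film reading is missing.

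The size of any bias is unknown. The rise from 2.5% to 6.6% or 15% rests on assumed misreading of 10% or 20% in one arm, 70% true clearance and 94 per arm; it shows sensitivity and is not an estimate for this trial. Masked film reading would not protect time to expulsion, on which the reported efficacy contrast rests. Separately from masking, the claim of fewer side effects is not supported by the report's own p of 0.315, and analgesic use does not establish efficacy in stone expulsion.

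**What to change.** **Film reading.** Label the 4-week X-ray KUB with the study number only. Have the existing reader record cleared or not cleared before the allocation list is opened, with the other investigator holding the list. For films already taken, re-read those that were retained in the same way.

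**Other outcomes.** In any continuation or repeat, ask about side effects, analgesic use and date of stone passage from one fixed checklist in both arms. This is only partial protection, because patients know their product. The questioning cannot be redone for patients already followed.

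**Report.** State who assessed each outcome and whether they knew the arm. Describe side effects, analgesic use and expulsion time as open-label, and do not claim superiority on these unmasked data alone. Remove the Conclusion's claim of fewer side effects and the Discussion's inference from analgesic use to efficacy. Mark any misreading illustration as an assumption, and do not offer the 18.1-point analgesic difference as a measure of assessment bias.

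**Cost.** A label, a one-page checklist, a fixed order of working, and a re-reading session if films were kept. Data entry is slightly slower and some patients may disclose their drug. The sample size stays at 208.

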	Mid	08(17.4%)	38(82.6%)	0.001
	Distal	41(51.9%)	38(48.1%)	
Water intake	Less than 1 litre	59(54.6%)	49(45.4%)	
	More than 1 litre	18(25.4%)	53(74.6%)	0.001
Analgesic requirement	Yes	26(61.9%)	16(38.1%)	0.005
	No	51(37.2%)	86(62.8%)	
Time for removal	Less than 14 days	6(10.3%)	52(89.7%)	
	14-21	14(27.5%)	37(72.5%)	0.001
	22-28	57(81.4%)	13(18.6%)	

presented as frequency and percentage with association

The table compares several factors along with the corresponding p-values to assess statistical significance between two drugs tamsulosin and silodosin.

First, based on Body Mass Index (BMI), 43.4% of those with a normal BMI were prescribed Tamsulosin, while 56.6% were recommended Silodosin. On the other hand, among those who were obese, 38.5% were given Tamsulosin and 61.5% were given Silodosin; p-value came out to be 0.730, which meant that there was no statistically significant variation in the medication preferences according to BMI.

15.2% of patients who had pain for more than a week prior to CT scan, received Tamsulosin while 84.8% received silodosin.

51.9% of the patients with proximal ureteric stone were given Tamsulosin and 48.1% received Silodosin.

82.6 percent of patients with mid-ureteric stone problems received Silodosin, while 17.4% received Tamsulosin.

51.9% of patients with distal ureteric stones received Tamsulosin and 48.1% on Silodosin.

Only 38.1% of patients on Silodosin required analgesics, whereas 61.9% of patients on Tamsulosin used analgesics.

89.7% of patients on silodosin had their stone removed in less than 14 days, while only 10.3% of the patients on Tamsulosin had their stone removed in aforementioned duration.

72.5% of patients on Silodosin had their stone removed in 14-21 days, while only 27.5% of the patients on Tamsulosin had their stone removed in same duration.

Moreover, 81.4% on Tamsulosin had their stone removed in 22-28 days and 18.6% patients on Silodosin had it removed in same duration.

		Tamsulosin	Silodosin	p- value
Side	None	61 (40.1%)	91(59.9%)	
effect	Othostatic	09 (60.0%)	06(40.0%)	
	hypotension			0.3.15
	Abnormal	2(66.7%)	1(33.3%)	
	ejaculation			
	Headache	5(55.6%)	4 (44.4%)	

Table 2 Association between Tamsulosin and Silodosin with side effects

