This bar chart presents a comparative examination of the rates of stone expulsion for patients who were suggested to take Tamsulosin or Silodosin during three distinct time periods—less than 14 days, 14–21 days, and 21–28 days.

The results are color-coded, with red bars denoting silodosin and blue bars denoting tamsulosin.

Silodosin shows a markedly greater efficacy in stone expulsion, with about 55 patients expulsing stone in less than 14 days in comparison to just about 5 patients on Tamsulosin.

This suggests that Silodosin is far more successful at facilitating stone removal in less time than Tamsulosin.

While in 14–21days duration, Silodosin continues to work better than Tamsulosin in removing stones. About 20 patients on Tamsulosin were able to successfully remove stone, compared to about 30 people on Silodosin. This implies that while tamsulosin is also beneficial, silodosin retains greater efficacy.

In the span of 21–28 days, 57 patients on Tamsulosin while 13 on Silodosin were able to eliminate stones. In general, Silodosin is quite successful for rapid stone ejection during the first two weeks. Using the intended period for stone

ejection to guide medicine selection, this time-dependent efficacy analysis offers clinicians important information.

[figure not shown]

Figure 3 Survival function

This statistical method is commonly used to estimate the time until an event occurs and to compare the survival curves of different groups. In this case, Kaplan–Meier analysis was performed to assess the duration that patients required to expel kidney stones while receiving either silodosin or tamsulosin treatment. The rate of the expulsion of stone and the time for it, for both groups, was evaluated using this method, as can be seen in Figure 2.

The log-rank test was applied to compare the rate and time for stone expulsion between the two groups. It is a hypothesis test for comparing the survival distributions of two samples. It was used in this study to see if patients treated with silodosin and those treated with tamsulosin had significantly different times for stones to be expelled. With a p-value of 0.05, the log-rank test findings showed that there was statistically significant difference between the two groups. This indicates that both groups' times to stone expulsion were statistically comparable.

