Similar results were seen in another study showing that, individuals receiving just tamsulosin treatment needed a greater average analgesic dosage of 391.43 \pm 165.60 mg with a p-value of 0.005, which denotes substantial significance, the necessary(50).

Similarly, a study showed statistically significant difference in the amount of analgesics needed by patients treated with Silodosin compared to those treated with tamsulosin only. The robustness of the conclusion was highlighted by the fact that the group receiving Silodosin treatment required considerably fewer analgesics than the groups receiving Tamsulosin, with a p-value of < 0.001(51).

Conclusion

An effective treatment for ureteral stones is medical expulsive therapy. According to our findings, silodosin has a safer profile and is more successful than tamsulosin at ejecting ureteric stones.

Silodosin had an increased rate of stone expulsion and took less time in stone expulsion compared to those treated with Tamsulosin.

In addition, patients treated with silodosin reported fewer side effects, such as a retrograde ejaculation, orthostatic hypotension and headaches as compared to those taking Tamsulosin.

In addition, those who received Silodosin needed less analgesic medication than those who received Tamsulosin.

•

REFERENCES

- Ahmed AFAM, Al-Sayed AYS. Tamsulosin versus Alfuzosin in the Treatment of Patients with Distal Ureteral Stones: Prospective, Randomized, Comparative Study. Korean J Urol. 2010 Mar;51(3):193–7.
- 5. Pietropaolo A, Proietti S, Geraghty R, Skolarikos A, Papatsoris A, Liatsikos E, et al. Trends of 'urolithiasis: interventions, simulation, and

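### The claim of faster stone expulsion rests on expulsion times that the plan does not collect and whose source the documents never state

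*Combined protocol and SAP*

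**What the plan says.** **Planned observation.** The data collection section schedules one outcome visit, with a binary record of whether the stone is gone: "The patients will be called for follow up at 4 weeks with an X-ray KUB without bowel preparation. We will note if the stone has" (the sentence closes with the two possible answers). The operational definitions match this: "Stone clearance will be defined as no evidence of stone on follow up X-ray KUB imaging at 4 weeks". The only other contact is initiated by the patient, who is told the "reasons for follow up earlier than four weeks including fever, persistent pain or gross hematuria". No date of passage, diary, urine straining, interim imaging or telephone contact is described.

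**Planned analysis.** The sample size section works from expulsion rates (58–64% on tamsulosin, 78–83% on silodosin, difference 19 points). The data analysis section names a t-test and no time-to-event method.

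**Reported.** The results table of study variables by drug has a row for time to removal in three bands, and the text below it states that "89.7% of patients on silodosin had their stone removed in less than 14 days". Under Figure 3, "Kaplan–Meier analysis was performed to assess the duration that patients required to expel kidney stones", followed by a log-rank test. The only efficacy figures in the abstract are expulsions before day 14 (about 55 v about 5 patients). The discussion lists the under-14-day figure as a main result, and the conclusion says silodosin "took less time in stone expulsion compared to those treated with Tamsulosin".

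**The concern.** A single film at day 28 shows whether the stone has gone by then. For a patient who has cleared, it says only that passage happened at some time from day 0 to day 28. It carries no information on which part of that window. The reported bands therefore need another source of data, and the documents name none.

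This matters because speed carries the reported efficacy case. If times were obtained in different ways in the two arms, or with different prompting, the difference in method would appear as a drug effect. No blinding is described that would guard against this. A reader cannot judge the risk without knowing how the times were ascertained.

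**Working it through.** **1. What the trial was sized for.** Take 59% v 78% (a 19-point difference within the stated ranges), two-sided 5%, power 80%, 1:1. Two-sidedness is an assumption, since the plan does not state it. With the pooled-variance formula and mean rate 0.685:

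n = [1.96·√(2·0.685·0.315) + 0.8416·√(0.59·0.41 + 0.78·0.22)]² / 0.19² = 92.6, so 93 per arm.

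93/0.9 = 103.3, so 104 per arm and 208 in total. The plan's figure is reproduced. It is a sample size for a binary rate, not for time to event.

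**2. Reported bands** (results table, row on time for removal):

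| Band (days) | Tamsulosin | Silodosin |
|---|---|---|
| <14 | 6 | 52 |
| 14–21 | 14 | 37 |
| 22–28 | 57 | 13 |
| Sum | 77 | 102 |

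77 + 102 = 179, the number of patients the results section says were analysed. Nobody is left for a category of stones not passed.

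**3. Within-arm figures.** Before day 14: 6/77 = 7.8% v 52/102 = 51.0%. By day 21: 20/77 = 26.0% v 89/102 = 87.3%. By day 28: 77/77 v 102/102, difference 0. The 89.7% in the text is 52/58, silodosin's share of the first band, not a rate among silodosin patients.

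**4. Against the planning rates.** Expected uncleared stones among these 179:
- upper rates: 77·0.36 + 102·0.17 = 45.1
- lower rates: 77·0.42 + 102·0.22 = 54.8

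The table shows none.

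**5. If uncleared stones were coded into the last band.** Four-week clearance could then lie anywhere from 20/77 = 26.0% to 100% on tamsulosin and from 89/102 = 87.3% to 100% on silodosin. The planned endpoint cannot be read from the table.

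**6. Log-rank on the bands**, each treated as one event time, tamsulosin arm:
- Expected: 58·77/179 + 51·71/121 + 70·57/70 = 24.95 + 29.93 + 57 = 111.88. Observed: 77.
- Variance: 58·(77/179)·(102/179)·(121/178) + 51·(71/121)·(50/121)·(70/120) + 0 = 9.66 + 7.21 = 16.88.
- Chi-square = (77 − 111.88)²/16.88 = 72.1, p about 2e-17.

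The text under Figure 3 gives p = 0.05. Coding of the last band does not explain the gap. The choice least favourable to a difference counts all 57 tamsulosin patients there as expelled and all 13 silodosin patients as censored. The last band then adds 57 − 57·57/70 = 10.59 to observed minus expected and 57·(57/70)·(13/70)·(13/69) = 1.62 to the variance. Chi-square = (−34.88 + 10.59)²/18.50 = 31.9, still far beyond 0.05.

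**7. How the log-rank result is described.** Within two paragraphs it is called a significant difference, then evidence that the times were comparable, then a difference that did not reach significance.

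**The case against.** The strongest reply is that the plan's list of data items is not exhaustive. The results tabulate income, BMI, water intake and analgesic use, none of which the data collection section names. Expulsion dates may likewise have been collected, even prospectively. This stands. A reader might infer that the times can only be patient recall at 4 weeks; the documents do not support that. They show an undocumented source, not a particular one. Nor do they support the inference that early visits over-represent patients whose stones had not passed, since no data on those visits are given.

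It is also fair to say that the single visit suits the planned endpoint, binary clearance at 4 weeks. The visit schedule is not defective for that purpose. The fault is a time analysis added without a documented means of collection.

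Two further replies carry less weight. The results text concedes in one place that the difference was not significant, but the abstract and the conclusion carry no such caution. And 0.05 may be the test's threshold rather than its p-value. In that case no log-rank p-value is reported at all, and the contradictory descriptions remain.

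**Conclusion.** The point holds. Followed as written, the plan yields cleared or not cleared at 4 weeks, and the three time bands cannot be built from that. The whole under-14-day contrast, 7.8% v 51.0%, depends on a variable that was not planned and whose ascertainment is not described. The reported log-rank result does not agree with the bands under any coding of the last band.

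A reader might go further and conclude that the drugs were equally effective because both arms reach 100%. That is not established either. It holds only if every patient in the 22–28 day band truly passed the stone and no uncleared stones were left out of the 179. The documents report no X-ray clearance by arm, so the planned comparison remains unknown.

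The figures assume the table's arm sizes of 77 and 102. The abstract gives 89 and 93 with a total of 180, and its early counts (about 55 v about 5) differ slightly from the table's 52 v 6. These differences would shift the percentages but not the conclusion.

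**What to change.** For the reported trial:

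1. Report, per arm, the number of stones cleared and not cleared on the 4-week X-ray, say how uncleared stones were coded in the time bands, and make this the efficacy result, as planned.
2. State how, when and by whom the expulsion times were ascertained. Do not label them recall unless that is confirmed.
3. Unless dated times collected in the same systematic way in both arms can be shown, present the bands and the Kaplan–Meier and log-rank analyses as unplanned and exploratory, and withdraw faster expulsion as a demonstrated finding in the abstract, discussion and conclusion.
4. Recompute the log-rank test from the individual times, reconcile it with the bands, and describe it in one consistent way.

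If the protocol is reused with a claim about time, have the date of passage recorded through the same scripted contact on fixed days in both arms, confirm clearance at the 4-week film, and analyse the times as interval-censored between contacts.

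For this trial the cost is retrieving the X-ray results and rewording, and the headline may shrink to no demonstrated difference. For a future trial it is a few short calls per patient.
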